7.9.3.6 Secondary Endpoint #6

Within-subject change of SF-36 quality of life questionnaire Mental Component Score (English language version), from baseline to 12 months following the Visualase procedure, categorized as -1 if the decrease is clinically significant (\leq -4.58), categorized as 0 if not clinically significant (-4.57 to +4.57), and categorized as +1 if the increase is clinically significant (\geq 4.58).

It is hypothesized that the SF-36 Mental Component Score (MCS) will increase (improve) from baseline to 12 months following the Visualase procedure. The hypotheses associated with this endpoint are as follows:

Null Hypothesis: M (V-SF-36 - BSL-SF-36-MCS) \leq 0 Alternate Hypothesis: M (V-SF-36 - BSL-SF-36-MCS) > 0

Where M (V- SF-36-MCS - BSL- SF-36-MCS) = sign-test statistic ([increases-decreases]/2) in the SF-36 quality of life questionnaire MCS from baseline to Month 12 post Visualase.

Revision 1.0 Page 15 of 23

A sign test will be used to determine if the median categorical change is significantly greater than zero. The MCID of 4.58 points for the SF-36-MCS is based on published literature (Wiebe 2002).

7.9.3.7 Secondary Endpoint #7

Within-subject change of SF-36 quality of life questionnaire Physical Component Score (English language version), from baseline to 12 months following the Visualase procedure, categorized as -1 if the decrease is clinically significant (\leq -3.02), categorized as 0 if not clinically significant (-3.01 to +3.01), and categorized as +1 if the increase is clinically significant (\geq 3.02).

It is hypothesized that the SF-36 Physical Component Score (PCS) will increase (improve) from baseline to 12 months following the Visualase procedure. The hypotheses associated with this endpoint are as follows:

Null Hypothesis: $M (V-SF-36-PCS - BSL-SF-36-PCS) \le 0$ Alternate Hypothesis: M (V-SF-36-PCS - BSL-SF-36-PCS) > 0

Where M (V-SF-36-PCS - BSL- SF-36-PCS) = sign-test statistic ([increases-decreases]/2) in the SF-36 quality of life questionnaire PCS from baseline to Month 12 post Visualase.

A sign test will be used to determine if the median categorical change is significantly greater than zero. The MCID of 3.02 points for the SF-36 Physical Component Score is based on published literature (Wiebe 2002).

7.9.3.8 Secondary Endpoint #8

Seizure freedom (defined as Engel Class I, Appendix 1) at 12 months following the Visualase procedure compared to historical reference threshold for open surgical resection

[figure not shown]
It is hypothesized that the seizure freedom at 12 months following the Visualase procedure will not be inferior to 64% reported in the literature for open surgical resection (Wiebe 2001). The hypotheses associated with this endpoint are as follows:

[figure not shown]
Null Hypothesis: $\pi V - 64\% + \delta \le 0$ Alternate Hypothesis: $\pi V - 64\% + \delta > 0$

Where πV is the proportion of subjects treated with Visualase experiencing no seizures.

An exact 95% CI for the percentage of subjects who are seizure free will be calculated and its lower boundary compared to zero after subtraction of the historical open surgical resection percentage of 64% and the addition of the equivalence delta percentage of 10% (Wiebe 2001).

[figure not shown]

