Two surgical resection techniques have been commonly utilized to treat mesial temporal epilepsy, namely anterior temporal lobectomy with mesial temporal resection (ATL) and selective amygdalohippocampectomy (SAH). Schramm reviewed 53 studies in which various temporal lobe resections were performed for medically intractable mesial temporal lobe epilepsies and found consistently high rates of seizure freedom at oneyear post-operative follow-up.9 In the most referenced randomized TLE study by Wiebe et al, seizure freedom occurred in 58% of the group assigned to surgery versus 8% for the patients who continued with medical therapy only. 10 A second randomized trial provided confirmation of these results; 73% of mesial TLE patients who underwent temporal lobe resection were seizure-free after 2 years compared to 0 patients with medical treatment. 11 Despite these, and many other well-documented high rates of seizure-freedom following surgical resection of temporal foci, the utilization of temporal lobectomy has not increased from 1990 to 200812 but has decreased, according to a recent survey. 13 Not only has surgery for epilepsy remained arguably the most underused of all proven effective therapies, even those patients who are referred for surgery wait for an average of 22 years after onset of epilepsy for that referral, 14 often too late to prevent or reverse the disabling adverse medical, psychological and social consequences of recurrent seizures. Factors like prolonged recovery, surgical invasiveness, and potential morbidities such as neurological deficits have been obstacles for completion of more epilepsy surgeries.

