7.5.1 Seizure Classification and Diary

Each subject's seizure types will be documented on the Seizure Classification eCRF, according to clinical manifestation and the subject's own description. A study Investigator will then classify seizure types per the International League Against Epilepsy (ILAE) classification. Seizure classification will initially be conducted after consent, prior to submission to the Pre-Surgical Evaluation Committee for review, and then amended throughout the subject's participation in the study if new seizure types occur.

Subjects will be given paper-based seizure diaries to document occurrence of seizures after enrollment through study exit. The seizure diary will be initially provided to the subject after consent, prior to submission to the Pre-Surgical Evaluation Committee. Seizure types will be recorded for each subject in concordance with the initial Seizure Classification eCRF. Seizure diaries will be reviewed with the subjects and collected by the site at specified visits. The site will enter seizure information into the Seizure Diary Summary eCRF. Recorded data shall include qualifiers needed to determine Engel Classification per Appendix C (e.g., nocturnal seizures only or generalized convulsion with AED discontinuation). A new seizure diary may be issued to the subject at each visit if needed.

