7.1.3.2 Modified Intent to Treat (mITT) Population

All subjects who enter the operating room and start the Visualase procedure (i.e., undergo scalp incision) will be included in the mITT analysis population. The mITT population will be the primary analysis population for efficacy evaluations.

Non-compliance is defined as any subjects who have not submitted enough seizure diaries or qualifiers in their seizure diaries through 12 months, from which the Engel I Classification could not be determined at study exit because of the missing information. The detail of the seizure diaries refers to section 7.5.1 of CIP.

SLATE Statistical Analysis Plan Revision 1.0 Page 9 of 23 Medtronic

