Appendix 1: Engel Classification of Postoperative Outcomeⁱ

Class I: Free of disabling seizures^a

- A. Completely seizure free since surgery
- B. Nondisabling simple partial seizures only since surgery
- C. Some disabling seizures after surgery, but free of disabling seizures for at least 2 years
- D. Generalized convulsions with AED discontinuation only

Class II: Rare disabling seizures ("almost seizure free")b

- A. Initially free of disabling seizures but has rare seizures now
- B. Rare disabling seizures since surgery
- C. More than rare disabling seizures since surgery, but rare seizures for the last 2 years
- D. Nocturnal seizures only

Class III: Worthwhile improvement^c

- A. Worthwhile seizure reduction
- B. Prolonged seizure-free intervals amounting to greater than half the followed-up period, but not <2 years

Class IV: No worthwhile improvement

- A. Significant seizure reduction
- B. No appreciable change
- C. Seizures worse

^aExcludes early postoperative seizures (first few weeks). This exclusion is quantitatively defined as 30 days for this protocol.

b"Rare" is quantitatively defined as ≤2 seizure days per year for this protocol.

^cDetermination of "worthwhile improvement" will require quantitative analysis of additional data such as percentage seizure reduction, cognitive function, and quality of life. This is defined as 80% reduction in seizures for this protocol.

Engel J. Outcome with respect to epileptic seizures. In *Surgical Treatment of the Epilepsies*, edited by J. Engel, Jr. Raven Press, New York. 1987

[figure not shown]
SLATE Statistical Analysis Plan		Form
Revision 1.0 Page 20 of 23		Medtronic

SLATE Statistical Analysis Plan Revision 1.0 Page 21 of 23 Medtronic

Revision 1.0

Page 22 of 23

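### Does the 64% open-resection reference for Secondary Endpoint #8 conflict with the 58% that the protocol reports for the same trial?

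*SAP*

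**What the plan says.** SAP section 7.9.3.8 states that seizure freedom at 12 months "will not be inferior to 64% reported in the literature for open surgical resection" and cites the 2001 randomized trial. The lower limit of the exact 95% confidence interval, minus 64% and plus a 10% delta, must exceed zero. Protocol section 14.6.8 sets the same 64% and 10% without naming a source.

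Protocol section 3.1 describes the same trial (protocol reference 10): "seizure freedom occurred in 58% of the group assigned to surgery versus 8% for the patients who continued with medical therapy only". SAP Secondary Endpoint #1 takes its 8% from this citation, and that figure agrees with section 3.1. Section 3.1 also reports a second randomized trial, in which "73% of mesial TLE patients who underwent temporal lobe resection were seizure-free after 2 years".

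On the device side, the endpoint is Engel Class I. SAP Appendix 1 places "Nondisabling simple partial seizures only since surgery" within that class and says of early postoperative seizures: "This exclusion is quantitatively defined as 30 days for this protocol". SAP section 7.9.3.8 then glosses the tested proportion with the phrase "is the proportion of subjects treated with Visualase experiencing no seizures". The analysis set, in SAP section 7.1.3.2, is defined by scalp incision: "All subjects who enter the operating room and start the Visualase procedure (i.e., undergo scalp incision) will be included in the mITT analysis population".

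**The concern.** The trial has no concurrent control, so for this endpoint the 64% is the entire comparator. A reader who follows the citation back to the protocol finds 58% instead. Nothing in the supplied text says whether the 64% describes patients assigned to surgery or patients operated on, which seizure-outcome rule it uses, or at what time it was measured. The section's own wording adds doubt, because Engel Class I and a count of subjects with no seizures are different things.

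This is also the only test against a resection seizure-freedom rate, and a pass would be read as non-inferiority to surgery. If Engel Class I with the 30-day exclusion were more lenient than the rule behind the 64%, the device could pass too easily, even though 64% is the larger number.

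**Working it through.** **Inputs.** 150 treated subjects, 56% expected rate, 43% primary threshold and 89% stated power (SAP section 6); exact two-sided 95% interval (SAP sections 7.2 and 7.9.3.8); reference 64% and margin 10% (SAP section 7.9.3.8); 58% and 8% for the cited trial (protocol section 3.1). All 150 outcomes are taken as observed.

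**Method.** Find the smallest count r whose Clopper-Pearson lower limit at n = 150 exceeds the bar. The chance of passing is P(X ≥ r), with X binomial(150, p).

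**The plan's own figure.** For the 43% bar, r = 77 (lower limit 43.05%). At p = 0.56 the power is 89.1%, which reproduces the stated 89%.

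**Endpoint #8 under each reference.**

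| Reference | Bar | r of 150 | Lower limit at r | Pass at 56% | Pass at 64% |
|---|---|---|---|---|---|
| 64% (as written) | 64 − 10 = 54% | 94 | 54.4% | 5.8% | 66.7% |
| 58% (protocol section 3.1) | 58 − 10 = 48% | 85 | 48.3% | 46.9% | 97.4% |

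The plan's figure costs the device 94 − 85 = 9 more successes than 58% would. With 64%, 93 successes give a lower limit of 53.7% and fail.

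**Can 58% and 64% both be right for one trial?** The rate among those assigned is f × (rate if operated) + (1 − f) × (rate if not operated), where f is the fraction operated. Suppose 64% is the rate among those operated.

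- If nobody left unoperated becomes seizure free: f = 0.58 / 0.64 = 0.906.
- If the unoperated do as well as the 8% on medical therapy: f = (0.58 − 0.08) / (0.64 − 0.08) = 0.50 / 0.56 = 0.893.

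So the figures fit together if roughly 9% to 11% of those assigned were not operated on. This shows compatibility only. The documents do not give f.

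**Effect of a mismatch in outcome rules.** Suppose the device rate is exactly 54% by the rule behind the 64%. The offset is an assumption.

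| Device rule relative to reference rule | Rate as counted | P(X ≥ 94) |
|---|---|---|
| 4 points stricter | 50% | 0.1% |
| 2 points stricter | 52% | 0.5% |
| matched | 54% | 2.0% |
| 2 points more lenient | 56% | 5.8% |
| 4 points more lenient | 58% | 14.1% |
| 6 points more lenient | 60% | 28.1% |

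The test is sensitive to a mismatch, but the documents support neither a size nor a direction. The 6-point gap between 58% and 64% is a difference between two resection rates, so it is not evidence about an outcome rule.

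**Device-side definition.** The endpoint sentence in SAP section 7.9.3.8 ties seizure freedom to Engel Class I in Appendix 1. Appendix 1 fixes the 30-day exclusion, and SAP section 7.9.2 gives the window for the same outcome as day 30 to day 365. The no-seizures gloss also appears under the primary efficacy endpoint and Secondary Endpoints #1 and #2. An analyst would count Engel Class I in all of them.

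**The case for a change.** The best case for a change is that a single-arm test is only as good as its reference, so the plan should say what the reference measures before outcomes are known. A stricter number taken under a harsher rule can still give a lenient test. Few subjects are involved: 2 points is 3 of 150. The remedy would also be cheap, namely a source check, a sentence and, if the rules differ, a supportive count from diaries that "document occurrence of seizures after enrollment through study exit".

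Part of this stands. The supplied text does not trace the 64%, and one sentence giving its group, outcome rule and follow-up time would help a reader. But that sentence would leave the reference, the 54% bar, the test and the analysis set as they are. The supportive table would be needed only if a source outside the documents showed a difference.

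The 73% adds little. It is a 2-year rate among patients who underwent resection, set beside a 58% among patients assigned to surgery and an endpoint at 12 months. A 15-point span built from those figures mixes time points and denominators, and a non-inferiority margin is not meant to cover the spread between trials.

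**Conclusion.** No change to the plan follows. The documents do not show that 64% is wrong. It has a different group label from the 58%, the two figures are arithmetically compatible, both documents use it identically, and it raises the pass mark from 85 to 94 of 150. An unreconciled figure that works against the device does not flatter the result.

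The exposure is also limited by position. Endpoint #8 is tested only after the primary efficacy endpoint and seven earlier secondary endpoints succeed, and at the planned 56% it would pass 5.8% of the time even without that gate. The device-side outcome is defined well enough to analyse despite the loose gloss.

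These figures assume 150 fully observed outcomes and the exact interval. The false-pass rates also assume offsets that the documents do not support, so they carry no weight in the conclusion. Whether the source counts outcomes as this trial does cannot be settled from the protocol and SAP. It is a caveat for interpreting a pass.

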7.10 Safety Evaluation

Adverse events (AEs) will be the primary source of data to evaluate the safety of the procedure. AEs will be coded to Medical Dictionary for Regulatory Activities (MedDRA) terms. The incidence of AEs classified by system organ class and preferred term will be summarized by the number and percentage of subjects with AEs and the number of events will be provided for each category as well. Incidence will report the occurrence (one or more times for a given event for a subject).

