7.17 Retreatment

Subjects who fail to achieve Engel Class I seizure freedom or whose procedure could not be completed as intended prior to discharge may be evaluated for retreatment. Retreatment is defined as a subsequent Visualase procedure after the subject's discharge following the initial Visualase procedure, to treat MTLE ipsilateral to the initial Visualase procedure and also within the temporal lobe. If it is determined that the ablation of additional tissue within the original target site may improve the outcome, the

justification for retreatment and supporting evidence will be entered on an eCRF and submitted to the Pre-Surgical Evaluation Committee for assessment per Section 7.12. Justification and supporting evidence for consideration of retreatment may include, but is not limited to, EEG demonstrating interictal and ictal discharges from the same temporal lobe, MRI showing no other lesions, same type of seizure behavior and auras, and no evidence of extra-temporal lesions.

If the Pre-Surgical Evaluation Committee disagrees with the recommendation for retreatment, the subject may continue participation in the study per their original follow-up schedule without retreatment. Alternatively, the subject may be withdrawn from the study.

If the committee agrees with the recommendation for retreatment, the subject may be scheduled for an additional Visualase procedure. Retreated subjects will have the same assessments at the same intervals as they would for an initial procedure. The new follow-up visit windows will be calculated based on the date of the retreatment Visualase procedure.

Subjects retreated with Visualase after the subject's discharge from the original Visualase procedure will be considered to have failed the primary efficacy endpoint. However, their data will contribute to specified secondary endpoints.

Subjects who undergo open resection after a Visualase procedure will be considered to have failed the primary efficacy endpoint. Seizure and AE data will be collected per the standard of care for the site.

Subjects who are retreated with Visualase or undergo open resection after a Visualase procedure will be followed for 12 months after the secondary procedure, or until the last enrolled subject completes Follow-up Visit 4 (12 months), whichever occurs first.

All subjects will be assessed for safety for the duration of their participation in this study, regardless of whether they are retreated.

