10.2 Adverse Event and Device Deficiency Assessment

10.2.1 Study Reportable Adverse Events

Adverse event definitions are provided in Table 6. To ensure all AEs that are potentially relevant to the SLATE study are collected, the following adverse events will be collected and reported to Medtronic during the study, starting from the time the subject signs the informed consent:

- Device-related AEs
- Procedure-related AEs
- Anesthesia-related AEs
- Epilepsy-related AEs
- All SAEs

Each AE must be recorded on a separate AE eCRF and include a description of the event, the diagnosis, date of event onset, the date the site became aware of the event, diagnostic tests and procedures performed, actions taken as a result of the event, relatedness and severity of the event and the outcome of the event. Subject deaths are also required to be reported. Refer to Section 10.5 for subject death collection and reporting requirements.

Documented pre-existing conditions are not considered AEs unless the nature or severity of the condition has worsened. Unavoidable events listed in Table 6 need not be reported unless the AE worsens or is present outside the stated timeframe post-procedure.

Seizures are inherent to the disease state of the target population of this study and are expected to continue in a portion of subjects after the Visualase procedure. While all seizures will be reported and captured in a seizure diary, they will not be reported as AEs unless there is a worsening in the nature, severity or degree of incidence, according to the Investigator's opinion. Following are examples of seizures that are reportable as AEs:

- Worsening in clinical manifestations (for example, subject began having falls with their seizures which was not previously a component)
- Seizure frequency is increased
- Subject experiences a new seizure type or non-epileptic seizure
- Seizure led to injury or death

Memory and naming decline are established risks following epilepsy surgery involving the temporal lobe. In standard ATL resections, changes in these cognitive scores are expected and consequently are not considered as adverse events unless the magnitude of change exceeds the site investigator's expectations.

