10.3 Adverse Event Classification and Device Deficiency Review and Reporting

All AEs and device deficiencies will be reviewed by a Medtronic representative for completeness and accuracy and will request clarification and/or additional information from the Investigator when necessary.

Adverse events will be classified according to the definitions provided in Table 6.

Medtronic will utilize MedDRA, the Medical Dictionary for Regulatory Activities, to assign a MedDRA term for each AE based on the information provided by the Investigator.

Regulatory reporting of AEs will be completed according to FDA requirements. Refer to Section 10.4 for a list of required Investigator and Medtronic reporting requirements and timeframes. It is the responsibility of the Investigator to abide by any additional AE reporting requirements stipulated by the IRB responsible for oversight of the study.

Appendix E contains the Foreseeable Adverse Event List (FAL), which is a list of AEs related to the system or procedure that have been observed in previous relevant

(epilepsy) studies and may be experienced by subjects. This list may help to assess if an AE is unexpected in nature.

For emergency contact regarding a UADE, SAE and/or SADE, contact a clinical study representative immediately (refer to the study contact list provided in the site's study documents binder/investigator site file or refer to the contact information provided in this CIP).

AEs and deaths will be classified according to the responsibilities and parameters outlined in Table 7 below.

Table 7: Adverse Event Classification Responsibilities

What is Classified?	Who Classifies?	Classification Parameters	
Timing of the Event	Investigator	Pre-operative, intra-operative or post-operative	
Relatedness	Investigator	Procedure Anesthesia Device (Visualase System) Epilepsy	
	Sponsor	Procedure Anesthesia Device (Visualase System) Epilepsy	
	Investigator	Serious adverse event	
Seriousness	Sponsor	Serious adverse event Unanticipated adverse device effect	
Carranita .	Investigator	Mild, moderate, or severe	
Severity	Sponsor	Mild, moderate, or severe	
Diagnosis	Investigator	Based on presenting signs and symptoms and other supporting data	
	Sponsor	MedDRA term assigned based on the data provided by Investigator	
Death Classification	Investigator	SUDEP	

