7.1.3.1 Safety Population

All subjects who sign a consent form (i.e., are enrolled) will be included in the safety population.

All summaries of safety data will be based on the safety population.

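### The descriptive AE tables in SAP 7.10 state no onset window, so under the plan's own rules they mix events before incision and after open resection with events after ablation, over a denominator of everyone who consented

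*SAP*

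**What the plan says.** SAP 7.10 gives the tables their purpose: "Adverse events (AEs) will be the primary source of data to evaluate the safety of the procedure". It then defines them: "The incidence of AEs classified by system organ class and preferred term will be summarized by the number and percentage of subjects with AEs", with event counts added. The counting rule is "Incidence will report the occurrence (one or more times for a given event for a subject"). The visible section gives no first or last onset date and no split by operative phase, relatedness or later surgery.

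Four other provisions decide what goes into such a table:

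- **Who is counted.** SAP 7.1.3.1: "All subjects who sign a consent form (i.e., are enrolled) will be included in the safety population". The same section then fixes the base for reporting: "All summaries of safety data will be based on the safety population". Protocol 14.3.1 uses the same population.
- **When collection starts.** Protocol 10.2.1 collects device-, procedure-, anesthesia- and epilepsy-related AEs and all SAEs, "starting from the time the subject signs the informed consent".
- **When it ends.** Protocol 7.19 puts all data up to a subject's exit into the analysis.
- **Later surgery.** Protocol 7.17: "Subjects who are retreated with Visualase or undergo open resection after a Visualase procedure will be followed for 12 months after the secondary procedure". That period is cut short if the study's final participant reaches the 12-month visit first. AE data after open resection are collected according to the site's standard of care.

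The information needed to separate the periods is already recorded. Each AE has an onset date (Protocol 10.2.1). The investigator classifies its timing as "Pre-operative, intra-operative or post-operative" (Protocol 10.3, Table 7). A Secondary Procedure form exists (Protocol 7.8, Table 4).

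**The concern.** A table offered as evidence on the safety of a procedure should count events that could follow from it, among people who had it. Read with the provisions above, this one combines epilepsy before any operation, the period after ablation, and the period after an open resection. Its denominator includes people who were never operated on.

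The sponsor seeks an expanded indication (Protocol 2.1), and the per-term percentages are the main description of harm beyond the single tested endpoint. A reader would take them as risks of laser ablation. They would not be, and the table itself would not show how far off they were or in which direction.

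**Working it through.** The plan states no figure for the AE tables, so there is none to reproduce directly. The figures that bear on them are the enrolment cap and the treated minimum.

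**Inputs from the documents** (Protocol 14.1, SAP 6): at least 150 treated, 30% assumed attrition before the procedure, up to 215 enrolled.

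**1. Enrolment cap.** 150 / (1 − 0.30) = 214.3, rounded up to 215. This agrees with the plan.

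**2. Denominator effect.** If enrolment reaches 215 and 150 are treated:

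- never incised: 215 − 150 = 65, and 65 / 215 = 30.2% of the safety population;
- multiplier on any percentage of strictly post-incision events: 150 / 215 = 0.698;
- example: 30 treated subjects with an AE are 30 / 150 = 20.0% of those treated, but 30 / 215 = 14.0% in the planned table.

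**3. Numerator effect.** The documents give no AE rates, so every rate here is an assumption for illustration:

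- p = 0.20 of treated subjects have an AE after incision and before any open resection;
- q = 0.02 to 0.10 of all consented subjects have a reportable AE before incision, or, if never treated, at any time;
- s = 0 to 0.15 of treated subjects later have open resection, and 0.20 of those have an AE after it;
- these events are independent.

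Subjects counted = 150 × [1 − (1 − q)(1 − p)(1 − 0.20s)] + 65q. The count in the ablation period alone is 150 × 0.20 = 30.

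| q | s | Treated, counted | Untreated, counted | Total | % of 215 | Counted with no AE in the ablation period |
|---|---|---|---|---|---|---|
| 0.02 | 0 | 32.4 | 1.3 | 33.7 | 15.7% | (33.7 − 30) / 33.7 = 11.0% |
| 0.05 | 0.10 | 38.3 | 3.25 | 41.5 | 19.3% | (41.5 − 30) / 41.5 = 27.8% |
| 0.10 | 0.15 | 45.2 | 6.5 | 51.7 | 24.1% | (51.7 − 30) / 51.7 = 42.0% |

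The comparison value is 20.0% of 150 throughout. The pooled figure falls below it in the first row and above it in the third. In the middle row it is close (19.3%), although more than a quarter of the subjects counted had no AE in the ablation period. The two errors offset each other there, so a plausible total is no reassurance.

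**The case against.** **Silence is not an instruction to pool.** SAP 7.10 neither orders pooling nor rules out splits. The public SAP also has gaps nearby: page markers go from 15 to 18, and sections 7.1.2, 7.4.2 and 7.7 do not appear. Withheld text may contain a breakdown. This stands as a limit: the point is about the visible text, and falls away to the extent that withheld text supplies a window. But the population and data-use rules are explicit, and followed as written they produce the pooled table.

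**The tested safety result is handled elsewhere.** A reader might infer that the primary safety test is contaminated by epilepsy events before incision or by craniotomy complications. The documents do not support that. SAP 4.2.1 and Appendix 2 limit the endpoint to moderate or severe device-, procedure- or anesthesia-related events through 12 months. Protocol Table 6 ties procedure-relatedness to the surgery in which the device was used. This objection stands in full, and the point is confined to descriptive tables with no test attached.

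**A second ablation is still this device.** A reader might infer that retreatment complications are wrongly charged to Visualase. Protocol 7.17 defines retreatment as a further Visualase procedure, so they belong in its total, and removing them could understate harm. What remains is that exposure to one and to two procedures cannot be told apart.

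**The pre-incision numerator is limited.** Only study-reportable events enter, and seizures count only if they worsen in the investigator's opinion. That is fair, and the actual size is unknown.

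**Conclusion.** The point holds for the descriptive AE tables. Under the visible rules they count any study-reportable AE from consent to exit, over all consented subjects. The resulting percentages are not risks of the procedure.

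The size that rests on the plan's own numbers is the dilution: post-incision percentages shrink by a factor of about 0.70 if 215 enrol and 150 are treated, and by less if fewer untreated subjects enrol. The numerator effect rests on assumed rates. Over the ranges shown, 11% to 42% of the subjects counted have no AE in the ablation period.

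A reader might infer that the tables exaggerate harm, or conversely that they are diluted and so flatter the device. Neither follows, because the two effects oppose each other and the documents give no rates to settle the net sign. This should be corrected before the analysis, but it does not affect the primary safety conclusion.

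**What to change.** In SAP 7.10, with a matching exception in SAP 7.1.3.1 and Protocol 14.3.1:

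- **(a)** List pre-operative AEs separately, over all consented subjects. Show relatedness here too, because anesthesia is induced before incision (Protocol 7.14) and a related event could begin then.
- **(b)** Make the main procedure-safety table AEs with onset from first scalp incision to study exit or open resection, whichever is first, over subjects who underwent incision (the mITT set). Give device-, procedure- and anesthesia-related events a sub-column.
- **(c)** Keep AEs after Visualase retreatment in that total, and repeat the table restricted to the period before retreatment.
- **(d)** Tabulate AEs after open resection separately, over the subjects who had it.

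Because (b) runs to exit and does not stop at 12 months, late AEs in subjects with no further surgery are kept, and every AE falls in a table.

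The cost is SAP wording, programming and a few more tables; no new data are needed. The denominator in (b) departs from the rule that all safety summaries use the consented population, so that rule must be changed openly. Protocol 14.2 requires an amendment only if a principal feature changes; otherwise the change and its reason go in the clinical study report.
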